Results of a single-center randomized, double-blinded, placebo-controlled trial of arginine therapy for children with VOE requiring hospitalization (1). A total of 56 children >3 years old admitted to CHRCO for VOE were enrolled between 2000-2008 in this NIH-supported arginine trial (**NHLBI K23 award HL-04386-**

05). Patients were consented within 24 hours of admission. Patients with significant liver, renal or neurological dysfunction, >10 VOE admissions/year or a history of narcotics dependence were excluded. A standardized treatment & monitoring program for VOE was followed. Average age was 13.9 ± 4 years (range 3.6-19 years), and 52% were female. 73% of the patients had Hb-SS, 18% had Hb-SC, and 9% carried S- β thalassemia. Patients received IV or oral arginine (0.1 gram/kg TID, N=28) or placebo (N=28) for 5 days or until discharge from the hospital. Two patients randomized to the arginine arm did not receive parenteral opioids and were excluded from the analysis. Narcotic records for 2 patients (randomized to placebo arm) were incomplete & were not included in the narcotic use analysis.

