Mitochondrial dysfunction in the platelets of SCD patients. In a pilot study, we isolated platelets from the blood of adult SCD patients & healthy African American volunteers. Comprehensive analysis of mitochondrial function demonstrated that SCD patients manifested mitochondrial dysfunction characterized by decreased complex V activity compared to healthy African American subjects (Fig 8). A decrease in complex V activity, the ATPase required for ATP generation by oxidative phosphorylation, potentially results in increased mitochondrial reactive oxygen species production (through electron buildup in complexes I-IV) and decreased ATP generation. Consistent with this, we have measured increased mitochondrial ROS generation in SCD platelets compared to healthy controls (Fig 9A-C).

Mitochondrial dysfunction in SCD patients can be mimicked by oxidative stress. To determine whether oxidative stress causes mitochondrial dysfunction in mitochondria of SCD patients, healthy human platelets were exposed to free hemoglobin in vitro, a generator of oxidants through auto-oxidation of heme. Free hemoglobin (100uM) caused a decrease in mitochondrial complex V activity, which was prevented when an antioxidant (TEMPOL; 250uM) was included in the incubation (Figure 10).

Collectively, these data suggest that platelets from SCD patients manifest mitochondrial dysfunction that is potentially propagated by oxidative stress. Information on ADMA and mitochondrial dysfunction will also provide insight into these 2 overlapping mechanisms.

***Blood volume obtained from children with SCD may sometimes vary due to difficult IV access. Studies run for research labs will be prioritized to arginine metabolome. Additional secondary tests will be analyzed based on available blood sample. Use of discarded samples saved up to 72 hours will also be used to run research specified labs only if needed.**

PARTICIPANT SELECTION

The research coordinator/study team will review the ED track board and daily admission logs, and approach patients for enrollment who meet the following inclusion criteria:

Inclusion Criteria

- Established diagnosis of sickle cell disease (all SCD genotypes)
- Age 3-21 years of age
- Pain requiring medical care in an acute care setting (ED, hospital ward, day hospital, clinic)

not attributable to non-sickle cell causes, that is moderate-to-severe treated with parenteral opioids

Exclusion Criteria

- Decision to discharge home from acute care setting.

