A study binder will be kept by the research coordinator/enrollers that will record the names and unique identification code of each patient approached for enrollment in an enrollment log. The names and demographic information (age, gender, Hb-genotype) of those who were approached and decline enrollment and the reason for declining (if known) will be recorded as approached/not enrolled. Age, gender and Hb-genotype information on patients screened by the study team/coordinator but found to be not eligible will also be collected. All study binders will be kept in a locked cabinet in the research office of the PED or Aflac coordinators and electronic files with any private health information (PHI) will be kept in a password protected CHOA supported division sharepoint site that is backed up nightly. Only members of the study team will have access to the study folder.

Randomization and Arginine/Placebo Administration

Arginine/Placebo will be administered in a blinded fashion. Using randomization lists prepared by the

research pharmacist, the research pharmacist at Egleston Children's Hospital will perform a block randomization for all CHOA sites, and study drug will be allocated to the patient TID until discharge. **Randomization will be stratified for hydroxyurea use to insure an equal number of patients on HU in all arms to minimize this as a potential confounder.** The patient, nurses, and physicians caring for the patient will be blinded as to which medication the patient is receiving.

Once written informed consent is obtained, and eligibility is confirmed by study staff, children and adolescents age 3-21 years will be randomized to one of following three study arms:

- 1) Standard L-arginine dose (100mg/kg IV TID)
- 2) One-time L-arginine loading dose (200mg/kg IV) plus the standard dose (100mg/kg IV TID)
- 3) Placebo (normal saline 1-2 ml/kg IV TID)

Upon enrolment, the patient's medical record is reviewed for CMP and creatinine testing in the past month in the past 12 months.

- If there are no measurements within the past 12 months or if either SGPT/ALT or creatinine were elevated in the past 12 months (meeting exclusion criteria), the current CMP results must be reviewed prior to dose administration. (Patient may be randomized; however, delivery of study drug should be held until CMP results are reviewed and no exclusion criteria are noted).

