The primary goal of this analysis is to compare the standard arginine treatment with placebo. The power analysis is based on this comparison. This sample size calculation is based on a two-sample two-sided t-test, with the objective of detecting a 55% reduction in opioid use from its mean value (4.1) in the placebo group based on the preliminary data generated from the recent [name] arginine trial (1). Based on these findings, the standard deviations are 2.0 and 4.1 (days) in the arginine and the placebo groups, respectively. A sample size of 33 subjects per group has 80% power to detect the treatment effect stated above on a two-sided test at the 0.05 significance level. A secondary goal is to compare the other arginine treatment arm (with a loading dose) to the placebo arm. Finally the two arginine treatments will be compared to determine if there is any difference or trend towards a difference when a loading dose is used that is superior to the standard arginine dose used with success in prior studies. Based on past experiences with arginine therapy, few patients withdrew from the study after the therapy was switched from oral to parenteral. Up to 150 patients will be enrolled, allowing for screen failures and study withdrawal, in order to insure randomization and study completion of 108 patients (36 per group) allowing for a 7% withdrawal rate. We did not adjust the sample size calculations for multiple comparisons as the power calculation only corresponds to the primary goal involving a single comparison of patients receiving the standard treatment or the placebo. We anticipate that the "loading dose" arm will be either the same or better than the standard dose. We will evaluate the efficacy and safety of this loading dose compared to the placebo group.

Each of the comparisons mentioned above will be conducted via a general linear model analysis. Predictors will include the treatment indicator, use of HU, age group, gender and the interactions of each of the last three covariates with the treatment indicator. By including interactions in the model we will be able to determine whether the treatment effect varies across subgroups of patients.

Assistance with statistical analysis and power calculation was provided by the Department of Biostatistics and Bioinformatics at the Rollins School of Public Health, Emory University, by [name] PhD, who will be the biostatistical consultant on this project.

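### Hb genotype is left out of the primary model although all genotypes are enrolled; adding it as one prespecified main effect is a modest, nearly free gain in precision

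*Combined protocol and SAP*

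**What the plan says.** The Statistical Analysis section applies one model to every arm comparison: "Each of the comparisons mentioned above will be conducted via a general linear model analysis". The covariates follow: "Predictors will include the treatment indicator, use of HU, age group, gender and the interactions of each of the last three covariates", each interacting with the treatment indicator. Genotype is named nowhere in that section, either as a covariate or in a sensitivity analysis.

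The first inclusion criterion is "Established diagnosis of sickle cell disease (all SCD genotypes". The enrollment-log text under Participant Selection treats genotype as routine information. It is recorded with age and gender for families who decline, and "Age, gender and Hb-genotype information on patients screened by the study team/coordinator but found to be not eligible will also be collected". An established diagnosis is required for entry, so genotype should be available for every randomized child.

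The Randomization section balances one factor: "Randomization will be stratified for hydroxyurea use to insure an equal number of patients on HU in all arms". Specific Aim 1 says the same.

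The background account of the earlier single-center trial gives the only genotype distribution in the documents: "73% of the patients had Hb-SS, 18% had Hb-SC, and 9% carried" S-β thalassemia.

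**The concern.** The trial mixes Hb-SS, Hb-SC and S-β thalassemia, and the introduction describes sickle cell disease as a group of genetic disorders that vary in features including severe pain. If children with different genotypes need different amounts of parenteral opioid, two things follow. First, the part of that difference not carried by HU use, age group or gender sits in the residual variance and widens the confidence interval. Second, neither the stratification nor the model deals with a chance difference in genotype mix between small arms, so the estimate from the one trial that is run can be shifted by it.

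The plan already accepts the reasoning for HU, which it stratifies on and adjusts for to limit confounding. It also adjusts for age group and gender, which the enrollment log lists beside genotype. No reason is given for treating genotype differently. At stake is some precision in a comparison planned at 80% power.

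**Working it through.** **Inputs**

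- Target difference: 55% of the placebo mean of 4.1 mg/kg (Statistical Analysis), so 0.55 × 4.1 = 2.255 mg/kg. Implied arginine mean: 4.1 − 2.255 = 1.845 mg/kg.
- SDs: 2.0 (arginine) and 4.1 (placebo), same section. The text labels them as days, but they match the earlier trial's SEMs in mg/kg: 0.4 × √26 = 2.04 and 0.8 × √26 = 4.08.
- Two-sided alpha 0.05; 33 per group calculated; 36 per group expected to complete.
- Non-SS share: 18% + 9% = 27%, from the earlier trial. That this trial will have the same mix is an assumption.
- Genotype effect on opioid use: not given. A range is assumed below.

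**1. The plan's own figure.** Mean variance = (2.0² + 4.1²)/2 = (4.00 + 16.81)/2 = 10.405, so the root-mean-square SD is 3.226. The normal-approximation sample size for 80% power is 33 per group, which reproduces the plan. Power at 33 is 81.0% by normal approximation and 79.4% by the Welch noncentral t. The stated figure stands and does not depend on covariates.

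**2. Power with a genotype term.** Multiply both SDs by √(1 − R²), where R² is the share of variance that genotype explains beyond the other covariates, and recompute Welch power at n = 36.

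**3. What each R² would require.** For a two-level factor with non-SS share 0.27 and a common SS/non-SS gap g, R² = g² × 0.27 × 0.73 / 10.405, so g = √(R² × 10.405 / 0.1971). This treats genotype as unrelated to the other covariates. If SS children use more opioid, the non-SS mean in the arginine arm is 1.845 − 0.73g.

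| R² | Power at 36 per arm | Gap g (mg/kg) | Implied non-SS arginine mean (mg/kg) |
|---|---|---|---|
| 0 | 82.9% | 0 | 1.85 |
| 2% | 83.6% | 1.03 | 1.10 |
| 5% | 84.7% | 1.62 | 0.66 |
| 10% | 86.6% | 2.30 | 0.17 |

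At 10% the non-SS children on arginine would need almost no opioid, so that row is an extreme.

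**4. Chance imbalance.** Randomization does not balance genotype, so the between-arm difference in non-SS share has SD √(2 × 0.27 × 0.73/36) = 0.105, or 10.5 percentage points. From the exact difference of two binomials, a gap of 10 points or more occurs with probability 0.35, and of 20 points or more with probability 0.046.

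**5. What an imbalance does.** The shift in the estimate is the gap in share times g. With a 10-point gap and g between 1.03 and 2.30, it is 0.10 to 0.23 mg/kg. The standard error at 36 per arm is 3.226 × √(2/36) = 0.76 mg/kg, so the shift is 0.14 to 0.30 of one standard error, or 4.6% to 10% of the 2.255 target.

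**The case against.** The strongest reply is that this is a covariate preference with an assumed payoff. The documents nowhere say that genotype predicts mg/kg opioid use among children already sick enough to receive parenteral opioids. The introduction speaks only of variable disease features, and the pilot account gives only the mix. This stands: the gain cannot be sized from the documents.

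A second reply also stands. The model already contains HU, age group and gender, so only what genotype adds beyond them counts. The two-sample calculation ignores these terms and the three treatment interactions, so 82.9% is a benchmark rather than the power of the planned model.

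A third reply concerns imbalance. Randomization keeps the estimate unbiased on average, and ordinary chance imbalance is already reflected in the standard error. A shift of at most about 0.3 standard errors is small, and the argument could be made for any unlisted baseline variable. This stands in large part. Genotype differs from an arbitrary variable in that the protocol deliberately admits all its levels and already logs it.

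The list of predictors might also be read as open-ended. That does not settle the matter, because a covariate chosen after unblinding lacks the credibility of one named beforehand.

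A reader might infer more than the documents support: that the primary comparison is biased, that its error rate is inflated, or that the sample size is wrong. None of these follows. Nor do large power gains. An R² of 20% would need a gap of about 3.25 mg/kg, and if SS children use more, the implied non-SS arginine mean would be 1.845 − 0.73 × 3.25 = −0.53 mg/kg, which is impossible. If non-SS children used more, that bound would not apply, but nothing in the documents suggests it.

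**Conclusion.** The point holds as a modest improvement. Genotype is fixed before randomization and varies in the enrolled population, but is handled by neither the stratification nor the model. The consequence is limited to possible lost precision and unadjusted chance imbalance in the realized sample.

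For a partial R² of 2% to 5%, the gain at 36 per arm is about 0.7 to 1.8 points of power; at the 10% extreme it is 3.7 points. These figures rest on the plan's SDs and target difference, the pilot's 27% non-SS share, an assumed genotype effect and a two-sample approximation. If genotype adds nothing beyond HU, age group and gender, there is no gain.

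**What to change.** In the Statistical Analysis section, add Hb genotype (Hb-SS versus other) to the general linear model as a main effect, without a treatment interaction, and state the coding before unblinding. State that the covariate list is complete.

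This needs no new assessment, because genotype belongs to the established diagnosis required at entry. The sample size stays as it is. If genotype proves non-prognostic, the loss is one degree of freedom out of roughly 70 in a two-arm comparison of 72 children.

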Vaso-occlusion is believed to be the root cause of sickle cell pain. NO is a free radical & a potent vasodilator (21) that regulates vascular homeostasis & plays a role in vaso-occlusive complications of SCD (1, 3, 22-27). NO has properties that can impact every aspect of SCD, from decreasing platelet activation & adhesion receptor expression on the vascular endothelium, to decreasing vascular smooth muscle proliferation, limiting ischemia-reperfusion injury, modulating endothelial proliferation, & regulating inflammation. Given the crucial role of NO depletion in endothelial dysfunction (28), it is not surprising that NO dysregulation is a common denominator among varied mechanisms of sickle vasculopathy (3, 10, 27). NO is produced in the endothelium from its obligate substrate L-arginine, which is converted to citrulline by a family of enzymes, the NO synthases (NOS) (21). Although NOS expression & activity is increased, SCD is characterized by a state of NO resistance, NO inactivation, & impaired NO bioavailability (27, 29, 30). Under conditions of increased hemolysis, inflammation or oxidative stress, the compensatory upregulation of NO likely becomes overwhelmed & ineffective. Vascular dysfunction is the end result, due to complex & multifactorial interactions (**Fig 1**) (2).

Normal arginine metabolism is impaired in SCD (2, 4, 31-34) for many reasons. We found that adults with SCD are arginine deficient at steady-state (3, 4), while children have plasma levels that are similar to normal controls (4). The altered arginine metabolome differs in children vs. adults (4). An arginine deficiency develops with age & is influenced by acute events & chronic end-organ damage. However plasma arginine concentration decreases significantly in both adults & children with VOE & acute chest syndrome (ACS), and is associated with low NO_x levels (4). Lowest arginine levels were found in children requiring admission for VOE (**Fig 2A**) (4), with arginine levels returning to baseline during convalescence in the hospital (**Fig 2B**). Of interest, low plasma arginine alone was a sensitive predictor for admission (4),

while NO_x levels were not, suggesting a function for arginine bioavailability in VOE severity that goes beyond NO. Arginine bioavailability may represent a novel objective metabolic biomarker of pain severity worth exploring further.

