Therapeutic Potential of Arginine Therapy in SCD. In transgenic mouse models of SCD, L-arginine supplementation inhibits the red cell Gardos channels (12), reduces red cell density (12, 13), improves perfusion, & reduces lung injury, microvascular vaso-occlusion & mortality (14-17). Arginine increases erythrocyte glutathione levels in both mouse (15) & human trials (18). Independent of SCD, low global arginine bioavailability is associated with major adverse cardiovascular events including mortality in patients screened for cardiovascular disease (45), mortality risk in malaria (46), & is associated with pulmonary hypertension risk (11, 33, 47). Rapid healing of leg ulcers was reported with IV **arginine**-butyrate in both SCD & thalassemia (48). Short term arginine therapy improved pulmonary hypertension in SCD (6), & acutely increases both plasma & exhaled NO when administered to ethnically matched normal controls & patients with VOE (5, 49). When arginine is given to SCD patients at steady-state, a paradoxical **decrease** in NO_x occurs (**Fig 3A**) that is not overcome by higher doses (**Fig 3B**)(5), clearly indicating that arginine is metabolized differently in SCD compared to controls. However, when arginine is given during VOE (**Fig 3B**), a robust dose-dependent increase in NO_x is observed. (**Fig 4**)(5) This indicates that arginine is also metabolized differently in SCD at steady-state compared to times of acute illness including pain and acute chest syndrome (4, 5, 49). These early observations may account for the negative outcome of the Comprehensive Sickle Cell Centers' (CSCC) arginine trial, particularly since the primary outcome measure of that study was an increase in plasma NO_x levels, when published data in fact

demonstrated a decrease in NO_x with arginine supplementation at baseline. Ultimately nutritional therapy like arginine may only be beneficial during a deficient state such as VOE.

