The mechanism of action for arginine therapy during VOE is UNKNOWN, although we have shown that children are metabolically different during VOE compared to baseline with respect to the arginine metabolome. Several biochemical & cellular effects of L-Arginine administration will be evaluated in order to provide mechanistic insight into potential benefits of arginine therapy based on pre-clinical data supporting each potential mechanism. Since no single mechanism occurs in isolation, multiple mechanism are likely. Blood will be drawn, and urine will be obtained, processed and stored for future analyses at the time of presentation prior to study drug delivery (day 0), on day 1 (drawn with routine am labs 12-36 hr after initiation of study drug) and then on day of 21st dose (day 7) and/or prior to discharge (or ED discharge, whichever comes first). Exhaled NO levels will be obtained at presentation and daily in children mature enough to perform the procedure based on ATS guidelines (76), or prior to discharge in the ED for those not admitted. Additional information on important clinical outcomes will also be collected. Bloodwork for safety/toxicity monitoring will also be obtained with study blood draws (see Specific Aim #2).

Potential Mechanisms Impacted by Arginine Therapy

- **Global arginine bioavailability (GAB) and the arginine metabolome:** (arginine, ornithine, citrulline, arginase, ADMA, arginase activity/concentration, creatine, urinary arginine/amino acids).

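### The efficacy model makes no use of Day 0 plasma arginine, a pre-dose measurement already planned; prespecifying it is a cheap optional gain, not the repair of an error

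*Combined protocol and SAP*

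**What the plan says.** **The model.** STATISTICAL ANALYSIS applies one general linear model to each comparison: "Predictors will include the treatment indicator, use of HU, age group, gender", with the interaction of each of the three covariates with treatment. The stated purpose of the interactions is to see whether the effect varies between subgroups. No baseline arginine term appears.

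**The measurement.** Specific Aim 3 has blood drawn "at the time of presentation prior to study drug delivery (day 0"). The laboratory schedule under Monitoring During Study marks the arginine metabolome at Day 0, and the panel under Study Labs includes plasma arginine. The note on blood volume before PARTICIPANT SELECTION gives the metabolome priority when the sample is small.

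**The background.**
- Mechanisms of Arginine Dysregulation reports that "low plasma arginine alone was a sensitive predictor for admission", that the lowest levels were in children who needed admission, and that arginine bioavailability may be a marker of pain severity. It adds that mechanisms lowering bioavailability may affect an individual's response.
- The loading-dose rationale says that mechanisms of arginine consumption may affect response.
- The hemolysis entry under Potential Mechanisms Impacted by Arginine Therapy says that the degree of hemolysis may affect both the severity of deficiency and the response.
- Therapeutic Potential of Arginine Therapy in SCD ends: "Ultimately nutritional therapy like arginine may only be beneficial during a deficient state such as VOE".

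**The concern.** The trial plans to hold, for most patients, a pre-treatment value that its own background connects with severity, and the efficacy analysis leaves it aside. If that value is related to opioid use within arms, the variation it explains stays in the error term, and a chance difference in baseline deficiency between arms of about 36 goes unadjusted.

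The same holds for effect variation. The background describes deficiency as varying among children with VOE and its causes as possibly affecting response, but the model examines variation only over HU, age group and gender. STUDY DESIGN AND METHODS and Aim 3 give no method for relating clinical response to baseline arginine.

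At stake is some power and a useful description of response, not the validity of the comparison.

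**Working it through.** **Inputs from STATISTICAL ANALYSIS**
- Effect: "the objective of detecting a 55% reduction in opioid use from its mean value (4.1) in the placebo group", so 0.55 × 4.1 = 2.255 mg/kg.
- Spread: "the standard deviations are 2.0 and 4.1 (days) in the arginine and the placebo groups". The unit label is days, but the values match the pilot's standard errors in mg/kg with 26 per arm: 0.4 × √26 = 2.04 and 0.8 × √26 = 4.08.
- Test: "on a two-sided test at the 0.05 significance level".
- Completers: 36 per group.

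**Assumed, not in the documents.** r is the within-arm correlation of Day 0 arginine with total opioid use, beyond HU, age group and gender. The range taken is 0.1 to 0.5.

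**Step 1: the plan's figure.** The plan states: "A sample size of 33 subjects per group has 80% power to detect the treatment effect stated above". By the normal approximation, n = (1.960 + 0.842)² × (2.0² + 4.1²) / 2.255² = 7.849 × 20.81 / 5.085 = 32.1, so 33. Power at 33 is 79.9% by the pooled t-test and 79.4% by the Welch test. The stated figure reproduces.

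**Step 2: no covariate, 36 per arm.** SE = √(20.81 / 36) = 0.760; Welch power is 82.9%. This is an unadjusted t-test, used as a reference, not the planned linear model.

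**Step 3: same correlation in both arms.** Each SD is multiplied by √(1 − r²).

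| r | SE | Power | Gain (points) |
|---|---|---|---|
| 0.1 | 0.756 | 83.2% | 0.4 |
| 0.2 | 0.745 | 84.4% | 1.5 |
| 0.3 | 0.725 | 86.2% | 3.3 |
| 0.4 | 0.697 | 88.8% | 5.9 |
| 0.5 | 0.658 | 91.9% | 9.0 |

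**Step 4: correlation in placebo only.** If treatment corrects deficiency, the relation may fade on arginine. The placebo slope is 4.1r per SD of the covariate, and with equal arms the common slope averages to half of that. The residual variances are then 16.81 × (1 − 0.75r²) on placebo and 4.0 + 16.81r²/4 on arginine, which sum to 20.81 − 16.81r²/2.

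| r (placebo) | Sum | SE | Power |
|---|---|---|---|
| 0.3 | 20.05 | 0.746 | 84.3% |
| 0.4 | 19.47 | 0.735 | 85.4% |
| 0.5 | 18.71 | 0.721 | 86.8% |

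The gain then stays below 4 points even at r = 0.5.

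**Step 5: missing values.** With a share m missing and complete cases only, the variance changes by the factor (1 − r²) / (1 − m). This equals 1 when m = r²: 9% missing cancels the gain at r = 0.3, and 1% at r = 0.1.

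**Step 6: chance imbalance.** One standard error of the arm difference in baseline arginine is √(2/36) = 0.24 SD. At r = 0.4, with a root-mean-square SD of √(20.81/2) = 3.226, it shifts the unadjusted difference by 0.2357 × 0.4 × 3.226 = 0.30 mg/kg, or 13% of 2.255. The unadjusted standard error already allows for this.

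**Step 7: treatment-by-arginine interaction.** Per SD of arginine, SE = √(20.81 / 36) = 0.760, so 80% power needs 2.802 × 0.760 = 2.13 mg/kg per SD, nearly the whole planned effect. With a median split the SE doubles, and an interaction as large as the main effect has about 32% power.

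**The case against.** **A reader might infer that precision is being lost.** The documents do not show this. They link low arginine to admission, not to mg/kg of opioid among enrolled patients. Entry requires moderate-to-severe pain treated with parenteral opioids and excludes patients already due for discharge home, so much of the admission contrast is removed by selection. Levels recover during the stay, and randomisation may come up to 24 hours after the first parenteral opioid, so Day 0 values may partly reflect timing. This stands. In reply, some enrolled patients may still go home from the ED (ED discharge rate is a secondary outcome), and in the pilot opioid use correlated with length of stay at 0.86. A link is plausible but indirect.

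**A reader might infer that the trial leaves its deficiency premise untested.** This goes too far. The sentence on a deficient state contrasts VOE with steady state, and every enrolled patient has VOE. The hemolysis passage is about the degree of hemolysis, not the arginine level. STUDY DESIGN AND METHODS does propose to study the metabolome together with clinical endpoints. What is missing is a stated method for response by baseline level.

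**The choice of covariate is open.** HU belongs in the model as the stratification factor. The documents report no correlation with opioid use for age group or gender, but none for arginine either. Arginine deficiency is said to develop with age, so age group may carry part of the same information, and the pain score at presentation is another available severity measure. This too stands: arginine is a reasonable candidate, not the only one.

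**Validity is untouched.** Leaving out a baseline covariate does not bias a randomised comparison.

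**Conclusion.** The point holds as a low-priority improvement. The efficacy model adjusts for, and examines effect variation over, HU, age group and gender only, and leaves out a pre-dose measurement that the background connects with severity. It is not an error: the comparison is unbiased and 33 per group reproduces.

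The possible gain at 36 per arm runs from 0.4 power points (r = 0.1) to about 9 (r = 0.5) if the correlation is the same in both arms. If it exists on placebo alone, the gain is 1.4 to 3.9 points at r = 0.3 to 0.5. Every value of r is an assumption, and the gain shrinks further to the extent that age group or HU carries the same information. An analysis of response by baseline arginine could be no more than exploratory at this size.

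**What to change.** Before unblinding, prespecify:

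1. **A covariate-adjusted model** for total parenteral opioid use and length of stay that adds Day 0 plasma arginine, continuous on the log scale, as a main effect. It can go into the planned model or, if the sponsor keeps that as primary, into a named sensitivity analysis.
2. **A missing-value rule**, either a missing-value indicator or single imputation from baseline data, so that no randomised patient is dropped. Without one, complete-case analysis cancels the gain once about r² of the values are missing.
3. **One exploratory analysis**, labelled as such: the treatment effect against continuous Day 0 arginine, reported as an estimate with its interval. State beside it that 36 per arm gives 80% power only for an interaction of about 2.1 mg/kg per SD.

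The cost is a few lines in the analysis plan and one or two degrees of freedom, with no new assay or visit. The drawback is that some Day 0 values will be missing where blood volume is short.
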